6.1 Telephone follow up (week 2)

6.2 Overview

A follow up telephone call will be conducted 2 weeks after the patient is enrolled in the study. The goal of this phone call is to identify adverse events, to assess medication adherence, and pregnancy surveillance in female patients. Patients who become pregnant during the study will be asked to stop taking the medication and they will be withdrawn from the study. The phone script and event questionnaire (to assess for adverse events) is contained in CRF 2 – Adverse Events Form.

7.1 Telephone follow up (week 4)

7.2 Overview

A follow up telephone call will be conducted 4 weeks after the patient is enrolled in the study. The goal of this phone call is to identify adverse events, to assess medication adherence, and pregnancy surveillance in female patients. Patients who become pregnant during the study will be asked to stop taking the medication and they will be withdrawn from the study. The phone script and event questionnaire (to assess for adverse events) is contained in CRF 2 – Adverse Events Form.

8.1 In-person follow up (week 8)

8.2 Overview

The participant will be scheduled to return for an in-person follow up 8 weeks after study initiation. It is likely that the participant will also need to visit the clinic for standard care. If no visit is indicated, the visit will be conducted for purely research purposes without billing for medical care or utilization of any institutional services.

8.3 Intake

The participant will be greeted by the SRC when they arrive at the clinic. Prior to phlebotomy the participant will be taken to a private area for data collection.

8.4 Medication Refills

If the participant meets criteria to remain in the study (see 7.2) RC2 will refill the participant's medication. RC2 will go over with the patient inhaler technique and dosing schedule to confirm that the participant is using the medication properly. Once medication has been given to the participant, they will be instructed to put their medication away.

8.5 Adherence Status Check

CRF 8 – 8 Week Adherence Status check identifies if the participant has remained adherent to study guidelines (at least 70% of doses and 15 pain diaries). CRF 8 – 8 Week Adherence Status will be filled out by RC2 as this requires that the RC visualize study medication in an unblinded fashion. If at any time the participant falls below the cut-off for medication or diaries, they will be re-instructed to bring them back to compliance.

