8.6 Data collection

8.6.1 Questionnaire

The 8-week questionnaire will include data regarding respiratory symptoms, medication adherence, health-related quality of life, adverse events, side effects, and pregnancy surveillance in female patients. Patients who become pregnant during the study will be asked to stop taking the medication and they will be withdrawn from the study. Once it is confirmed by RC2 that the participant will remain in the study, CRF 5 – 8 Week Data Collection will be administered by the SRC.

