10.3 Collection of study medication

RC2 will collect the participants study medication once they are brought to a private area. CRF 9 – 16 Adherence Status will be filled out by RC2 to document medication adherence. If at any time the participant falls below the cut-off for medication or diaries, they will be re-instructed to bring them back to compliance.

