10.5 Data collection

The 16-week questionnaire will include data regarding respiratory symptoms, medication adherence, health-related quality of life, adverse events, side effects, and pregnancy surveillance in female patients. Patients who become pregnant during the study will be asked to stop taking the medication and they will be withdrawn from the study. Once it is confirmed by RC2 that the participant will remain in the study, CRF 6 – End of Study Questionnaire will be administered by the SRC.

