14.4 Aim 2: Primary and Secondary Outcomes: This aim will assess changes in pulmonary inflammation and vascular injury with ICS therapy. The primary outcomes for the trial will be **change in eNO (pulmonary inflammation) and sVCAM (vascular injury)** level 8 weeks after randomization. Secondary outcomes will be change in reticulocyte index, change in FEV₁/FVC ratio (expressed as percent predicted) and change in other key biomarkers.

14.5 Data Analysis: *Preliminary analyses* - Descriptive analyses for all socio-demographic and clinical variables will be performed. Preliminary data analyses will focus on examination of the distributional characteristics of measures used in the study. In this step, decisions will be made regarding possible transformations that might be required to meet the assumptions of the statistical tests that will be employed. Baseline values for individuals in each randomization assignment will be compared using t-tests, chi-square and non-parametric tests when appropriate. For outcomes that may be used in a definitive trial, univariate analyses will be performed first followed by stratified analyses with potential confounders (variables known or suspected to have associations with the frequency of painful episodes including age, gender, genotype, baseline hemoglobin, leukocyte count, and fetal hemoglobin percent). Potential confounders with p-value less than 0.2 will be included in parsimonious models.

14.6 Primary analyses: The primary outcome, **feasibility** as well as retention/recruitment rates, attrition points and adherence will be expressed for those enrolled from the ED and the hematology clinic. Feasibility measures will be compared between those enrolled in the ED vs. clinic using χ^2 statistics. Adherence (defined as use of greater than 70% of indicated doses by dosage counter) will be compared to the previously validated MARS-A score cutoff of 4.5 with a χ^2 statistic to validate the use of MARS-A in SCD.

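### At weeks 8 and 16 the inhaler is checked before participants report their adherence, so the MARS-A validation in section 14.6 is not assured an independent self-report

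*Combined protocol and SAP*

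**What the plan says.** **Week 8.** Section 8.5 has RC2 complete CRF 8 by inspecting the inhaler: the form "will be filled out by RC2 as this requires that the RC visualize study medication in an unblinded fashion". The same section continues: "If at any time the participant falls below the cut-off for medication or diaries, they will be re-instructed to bring them back to compliance". Section 8.4 adds a further contact about dosing, at refill: "RC2 will go over with the patient inhaler technique and dosing schedule to confirm that the participant is using the medication properly". Section 8.6.1 describes the content of the questionnaire: "The 8-week questionnaire will include data regarding respiratory symptoms, medication adherence, health-related quality of life". It also fixes the order: "Once it is confirmed by RC2 that the participant will remain in the study, CRF 5" is then administered by the SRC.

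**Week 16.** Section 10.3 begins "RC2 will collect the participants study medication once they are brought to a private area", has RC2 complete CRF 9, and repeats the re-instruction sentence. Section 10.5 says "The 16-week questionnaire will include data regarding respiratory symptoms, medication adherence, health-related quality of life", and again places CRF 6 after RC2's confirmation.

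**Analysis.** Section 14.6 defines adherence as more than 70% of doses on the counter and compares it with a MARS-A cutoff of 4.5 by a chi-square statistic, "to validate the use of MARS-A in SCD". It names neither the visit nor the form that supplies the MARS-A score.

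**The concern.** A validation study needs the index measure (self-report) to be obtained without influence from the reference measure (the counter). Here the stated sequence is the reverse. By the time participants answer adherence questions, a staff member has inspected the inhaler and, at week 16, taken it away. Those below the cut-off may also have been corrected.

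Knowing that staff hold the count gives a participant a reason to answer differently: more candidly, which raises agreement with the counter, or more defensively, which lowers it. Either way, the agreement found here may not carry over to a setting where MARS-A is used without a prior counter check. No section protects the self-report from this.

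**Working it through.** The plan gives no sample size, power or accuracy target for the MARS-A comparison, so there is no figure to reproduce. The check is a trace of the visit order, followed by an illustration.

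**1. What is stated and what is inferred**

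| Step | Week 8 | Week 16 | Status |
|---|---|---|---|
| RC2 inspects the inhaler and completes the adherence form | 8.5, CRF 8 | 10.3, CRF 9 | Stated |
| RC2 confirms continuation | 8.6.1 | 10.5 | Stated; that it rests on the inhaler check is inferred |
| SRC gives the questionnaire with adherence items, after the confirmation | 8.6.1, CRF 5 | 10.5, CRF 6 | Stated |
| Re-instruction below the cut-off | 8.5 | 10.3 | Stated to occur; person and moment not stated |
| MARS-A score | none named | none named | CRF 5/6 inferred |

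The second row's inference is reasonable. The adherence check is the only RC2 procedure described that could supply the week-8 confirmation, and the table of contents lists criteria to remain in the study where the body now has the adherence check.

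The inference that MARS-A sits on CRF 5/6 is also reasonable. The adherence forms are completed only at weeks 8 and 16, and only those two visit questionnaires are said to cover medication adherence; the week-20 list in section 11.4 omits it. The calls at weeks 2, 4 and 12 also assess adherence, but their script is in the adverse events form (CRF 2). A score from week 2 or 4 would cover a shorter dosing period than the week-8 counter.

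**2. Illustration on kappa.** All cells are assumed: 45 participants, 15 non-adherent by counter, and 3 of the 30 adherent scoring below 4.5. Kappa = (po − pe)/(1 − pe).

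- *Asked first, 6 of 15 non-adherent score low.* Sensitivity 6/15 = 40%. po = (6 + 27)/45 = 0.733; pe = (9×15 + 36×30)/45² = 0.600; kappa = 0.133/0.400 = 0.33.
- *Four of the nine over-reporters answer candidly after the check, so 10 of 15.* Sensitivity 67%. po = (10 + 27)/45 = 0.822; pe = (13×15 + 32×30)/45² = 0.570; kappa = 0.252/0.430 = 0.59.
- *Four of the six candid reporters turn defensive, so 2 of 15.* Sensitivity 13%. po = (2 + 27)/45 = 0.644; pe = (5×15 + 40×30)/45² = 0.630; kappa = 30/750 = 0.04.

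The differences from 0.33 are due to the order; the 0.33 itself is not.

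**3. Illustration on the chi-square test.** Assumptions: N = 45 or 50 (the planned sample and the week-8 number expected in Table 1), 50% or 70% adherent by counter, P(MARS-A ≥ 4.5 | adherent) = 0.70, two-sided alpha 0.05. Power = Φ((|p1 − p2| − 1.96·SE0)/SE1), with SE0 pooled and SE1 unpooled. For example, with 23 and 22 participants and 0.50 against 0.70, SE0 = 0.146 and SE1 = 0.143, so power = Φ(−0.61) = 0.27. Ranges are over the four combinations of N and adherence.

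| True P(MARS-A ≥ 4.5 given non-adherent) | Shift after the check | Chance of a significant result |
|---|---|---|
| 0.50 | none | 0.26 to 0.30 |
| 0.50 | −0.15 (more candid) | 0.60 to 0.71 |
| 0.50 | −0.30 (more candid) | 0.92 to 0.97 |
| 0.50 | +0.15 (defensive) | about 0.05 |
| 0.70 (uninformative) | none | 0.05 |
| 0.70 (uninformative) | −0.15 (more candid) | 0.17 to 0.19 |
| 0.70 (uninformative) | −0.30 (more candid) | 0.48 to 0.57 |

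At this sample size a modest shift in the answers of non-adherent participants could decide the result, in either direction.

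**The case against.** The strongest reply is that the documents fix less than a reader might infer.

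- **Timing of feedback.** It is tempting to read sections 8.5 and 10.3 as saying that participants are told their count and corrected just before they answer. They do not. The sentence is passive and open as to time. Section order cannot settle it, since refill (8.4) is printed before the check (8.5) although refill depends on meeting the criteria to remain. This stands. What survives is that the inspection itself precedes the questionnaire.
- **Place of MARS-A.** Section 14.6 does not tie it to CRF 5/6, and a score taken by telephone at week 2 or 4 would precede any scheduled counter reading. This stands as a gap in the plan; if the calls were intended, section 14.6 should say so.
- **Nothing new is disclosed.** Orientation Module A teaches mometasone participants to read the counter, and they can expect an inspection. This stands in part: asking first would not give a wholly unprompted answer, but it would remove the influence of an inspection just made and of any correction.
- **Week 16.** Section 10.1 ends study dosing at that visit, so the repeated re-instruction sentence has no study doses left to act on. This stands, and the two sections should be reconciled. The inhaler is still checked before CRF 6.
- **Importance.** The MARS-A comparison is ancillary. This stands and limits the weight of the point.

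**Conclusion.** The point holds in a limited form. If the stated sequence is followed, self-reported adherence is collected after RC2's inhaler check at both visits, and that counter is the reference for validating MARS-A. Independence of the two measures is not assured. This rests on two inferences: that MARS-A is on CRF 5/6, and that RC2's confirmation rests on the adherence check.

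A reader might go further and conclude that the validation is contaminated, that agreement is inflated, or that any apparent validity is produced by the visit order. The documents do not support this. Inflation is plausible, but the direction and size of the bias cannot be determined from them. The kappa and power figures come from assumed rates, and even under those a kappa of 0.33 is present before any order effect. Nor can it be concluded that symptom and quality-of-life answers on the same forms are distorted by a corrective talk, since the plan does not place that talk before the questionnaire.

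The primary feasibility outcome (counter and diaries, section 14.2) and the eNO and sVCAM outcomes (section 14.4) do not use MARS-A and are not affected. This is a cheap improvement to a secondary analysis.

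**What to change.** 1. In sections 8 and 10, have the SRC administer the CRF 5/6 adherence (MARS-A) items at intake, before RC2 reads the counter or anyone gives feedback on adherence. RC2 then completes CRF 8/9 and the remaining steps.
2. In section 14.6, name the visit and CRF that supply the MARS-A score.
3. Restrict the validation to scores obtained before that visit's counter check. Report week 8 and week 16 separately, since a week-16 answer follows the week-8 check whatever the order within the visit.
4. For data already collected, report the order as a limitation. The change log gives October 2016 as the end of data collection.

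The cost is small: same staff, forms and visits. The questionnaire would no longer wait for RC2's confirmation. That condition serves little remaining purpose, because the November 2015 change keeps non-adherent participants in follow-up to week 16. The manual change needs the usual approval, including the DSMB's approval of protocol alterations under section 1.4.3.

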8.6 Data collection

8.6.1 Questionnaire

The 8-week questionnaire will include data regarding respiratory symptoms, medication adherence, health-related quality of life, adverse events, side effects, and pregnancy surveillance in female patients. Patients who become pregnant during the study will be asked to stop taking the medication and they will be withdrawn from the study. Once it is confirmed by RC2 that the participant will remain in the study, CRF 5 – 8 Week Data Collection will be administered by the SRC.

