SCC staff ensures that clinic site staff are properly trained, that performance of the required procedures are monitored, and that deviations from the protocol or from study norms are investigated. Routine site monitoring reports, including patient recruitment, performance of follow-up visits, and protocol compliance, will be produced at regular intervals. For spirometry, the SRC's past 10 PFT results will be reviewed to ensure reproducibility of results.

- **Quality assurance procedures**

SCC staff will conduct quality assurance audits for every 5 participants enrolled in the study. In addition, quality assurance procedures and programs will be developed and implemented for laboratory determinations, for data collection, and for data entry.

- **Randomization**

SCC staff have developed and implemented an adaptive, biased coin, covariate balanced randomization algorithm. The algorithm is implemented using a windows laptop running the program 'R' which will be carried on the IMPROVE research cart.

After screening for eligibility is complete, participants will be randomized. The Randomization algorithm will balance participants based on whether or not they take hydroxyurea and by the number of ED visits for pain during the preceding year (this variable will be trichotomized: 0-5, 6-10, 11-15).

- **Data and Safety Monitoring Board (DSMB) functions and reports**

SCC staff will prepare reports for the DSMB and will respond to ad hoc queries from the DSMB. SCC staff developed the study monitoring plan, which indicates when interim monitoring of the efficacy outcomes will be performed, how adverse events will be reported, as well as the content of the DSMB reports. The DSMB reports will include tabulations and graphical presentation of administrative data (e.g., recruitment, compliance with therapy schedule, completion of follow-up procedures, and submission of data to the SCC), efficacy data (e.g., primary and secondary outcomes of the study, as required by the monitoring plan), and safety data (e.g., the occurrence of adverse events and serious adverse events).

- **Statistical analysis plan**

[figure not shown]
SCC staff developed the statistical analysis plan, which indicates, in detail, the main analysis for the primary outcome (including intention-to-treat analyses), secondary analyses, and analyses of the secondary and safety outcomes. In addition, the plan includes the frequency of DSMB reports, and how missing data will be handled.

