- d. They answer yes to questions 12 , 14, 15 and >15 for question 13 in group 5

Investigator Approval of Eligibility: _____ Date: _____

Supplement 3: Inhaler training and adherence modules

(Affix Label Here)
 
Participant ID: _
	
Date Form Filled Out:
 
-----
 
day month year
	
Inhaled Mometasone to Promote Reduction of Vaso-occlusive Events

---	---	---

Protocol Orientation Module A

If you lose your medication

Contact study staff immediately:

[REDACTED]
[REDACTED]
[REDACTED]
[REDACTED]
[REDACTED]

Pain diaries

Pain diaries are included in your package. Try to fill out a pain diary every day. If you miss a day that's ok. You must fill out at least 30 diaries to stay in the study.

Your medicine

This package contains your medicine for this study. Take one puff of the medicine every day. The research coordinator will teach you how to use the inhaler.

(Affix Label Here) Participant ID: _____	Date Form Filled Out: - - - - - day month year	Inhaled Mometasone to Promote Reduction of Vaso-occlusive Events
--	--	--

**Protocol Orientation Module: Adapted from “BREATHE EASIER: AN
ADULT ASTHMA EDUCATION PROGRAM” and Mometasone
Package Insert**

“Breathe Easier”

Developed by the American Institutes for Research and
the Kaiser-Permanente Medical Group

National Heart, Lung, and Blood Institute

National Institutes of Health

National Asthma Education and Prevention Program

FOR ORAL INHALATION ONLY

Please read this leaflet carefully before taking this medication

This leaflet does not contain the complete information about this medication. If you have any questions about mometasone inhalation ask your health care provider or pharmacist.

IMPORTANT POINTS TO REMEMBER

- Use this medication regularly and at the same time each day, as prescribed by your health care provider. You or your child may not get the most benefit for 1 to 2 weeks or longer after starting the medication. If you or your child's symptoms do not improve in that time frame or if your condition gets worse, contact your health care provider.
- The cap is needed to use the TWISTHALER. Do not twist the mouthpiece with your hand. When the cap is removed from the TWISTHALER, the dose counter will count down by one, and show the number of doses available after this use.

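### Week-8 and week-16 questionnaires depend on an unblinded coordinator confirming retention, which conflicts with the re-instruct-only rule, follow-up of non-adherent participants and the intention-to-treat aim

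*Combined protocol and SAP*

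**What the plan says.** Three places in the body make something conditional on staying in the study.

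- **8.6.1 (week 8):** "Once it is confirmed by RC2 that the participant will remain in the study", CRF 5 is administered.
- **10.5 (week 16):** "Once it is confirmed by RC2 that the participant will remain in the study, CRF 6" is administered.
- **8.4 (refill):** "If the participant meets criteria to remain in the study (see 7.2) RC2 will refill" the medication.

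Protocol Orientation Modules A and B in Supplement 3 tell participants: "You must fill out at least 30 diaries to stay in the study".

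Other places say something different. Section 8.5 sets the week-8 cut-off at 70% of doses and 15 diaries and states one consequence for falling below it: "they will be re-instructed to bring them back to compliance". Section 10.3 repeats that consequence at week 16. Neither mentions removal. The 11/18/2015 entry in the schedule of changes, which carries the document's own version date, records that non-adherent participants are now followed to 16 weeks. Section 2.3 says the analysis plan covers "the main analysis for the primary outcome (including intention-to-treat analyses").

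**The concern.** RC2 knows the treatment arm (4.3, 5.3.4.1) and completes the adherence forms CRF 8 and CRF 9. If the confirmation in 8.6.1 and 10.5 is a judgement on adherence, then whether a participant is asked about quality of life, respiratory symptoms, side effects and adverse events depends on behaviour after randomization, assessed by someone who is not blinded. The arms use different devices (a twisthaler and a metered dose inhaler, 4.3), so adherence, and with it the missing questionnaires, need not be balanced between arms.

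These answers matter to the study's purpose. Section 14.3 lists change in ASCQ-Me score, respiratory symptoms and safety among the candidate outcomes for a definitive trial. A participant who stopped the inhaler because of side effects is one whose CRF 5 is informative, and a literal reading could leave that form blank.

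The leaflet raises a related problem. Retention and points of attrition are feasibility measures in 14.2. A participant who is behind on diaries and believes the leaflet could conclude that participation is over, although no section of the manual body removes anyone for that reason.

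**Working it through.** No stated figure is in dispute, so the check sets the passages side by side.

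**1. Where does 8.4 point?** Section 7.2 is the week-4 telephone call. It covers adverse events, adherence and pregnancy. Its only withdrawal rule is pregnancy; it has no adherence or diary criterion. Other cross-references also lag behind the numbering: 8.6.2 to 8.6.4 cite 5.2.4.4 to 5.2.4.6, while those procedures stand at 5.3.4.4 to 5.3.4.6. The pointer to 7.2 is therefore plausibly out of date. The contents list an entry on criteria to remain between refills and data collection; in the body that position is held by 8.5, Adherence Status Check. That suggests, without proving, that the criteria once meant were adherence criteria.

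**2. What grounds for leaving does the body state?** Pregnancy (6.2, 7.2, 8.6.1, 9.2, 10.5, 11.4), adverse events (16.0, 17.0) and unwillingness to participate (16.0). Low adherence and few diaries are not among them.

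**3. Do the diary numbers conflict, or only the consequences?** With one diary a day:

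- Week 8: 15 diaries / (8 × 7 = 56 days) = 26.8%.
- Week 16: 30 diaries / (16 × 7 = 112 days) = 26.8%.

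The rates agree if the leaflet's 30 is meant over 16 weeks. The leaflet gives no period and comes in the first 8-week packet; read over 56 days, 30 would be 53.6%. On either reading the consequence differs: leaving the study in the leaflet, re-instruction in 8.5 and 10.3.

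**4. What is conditional, and what is not?**

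| Item | Section | Expressly conditional? |
|---|---|---|
| CRF 5 | 8.6.1 | Yes |
| CRF 6 | 10.5 | Yes |
| Refill | 8.4 | Yes, on unstated criteria |
| Serum, spirometry, eNO at week 8 | 8.6.2–8.6.4 | No |
| Pain diaries | 8.7, 10.6 | No |
| CRF 8, CRF 9 (adherence) | 8.5, 10.3 | No |
| Telephone calls (CRF 2) | 6.2, 7.2, 9.2 | No |

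**5. How many questionnaires?** The documents give no expected proportion below the cut-offs, so the proportion is assumed. With 45 participants allocated 2:1 (30 and 15), and the same proportion below in each arm:

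- 10%: 0.10 × 45 = 4.5
- 20%: 0.20 × 45 = 9 (6 and 3)
- 40%: 0.40 × 45 = 18 (12 and 6)

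These would be the missing questionnaires at one visit if the condition were applied to everyone below a cut-off.

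**The case against.** The strongest reply is that the RC2 clause concerns pregnancy only. The sentence before it, in both 8.6.1 and 10.5, is the pregnancy withdrawal rule; 7.2 contains the same rule; and 8.5 gives RC2 no adherence ground for withholding a form. This reading is possible but weak. Pregnancy surveillance is part of the questionnaire being withheld, so it cannot readily be its precondition. RC2's stated week-8 tasks are the unblinded adherence check and the refill. The reading also leaves the leaflet in conflict with 8.5.

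A second reply is that the intended practice is clear. The schedule of changes says that, even under the previous rule, non-adherent participants were in the intention-to-treat analyses and their 8-week questionnaires, clinical data, spirometry, eNO and blood were collected. This stands as evidence of intent. It means the documents do not support the inference that non-adherent participants would in fact give no questionnaire data. It does not remove the condition from the sections that staff follow.

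Third, the exposure is limited, and that also stands. A reader might infer that eNO power falls, or that intention-to-treat becomes per-protocol for the primary outcomes. Neither follows. eNO and sVCAM are collected under sections with no condition. Feasibility (14.2) rests on follow-up, diaries and dose counts; the diaries and adherence forms are not conditional, and a non-adherent participant counts as a failure whether or not CRF 5 is given.

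Finally, the effect of the leaflet on retention is a possibility, not a documented fact, and the same leaflet tolerates missed days. At week 16 the condition has little practical meaning, since study medication is being collected.

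**Conclusion.** The inconsistency is real and lies within the current text: 8.4, 8.6.1, 10.5 and both leaflets treat staying in the study as something still to be earned, while 8.5 and 10.3 do not. On a literal reading, the outcomes at risk are those on CRF 5 and CRF 6: ASCQ-Me quality of life, respiratory symptoms, side effects, and adverse events recorded on those forms. The main harm is selection of adherent participants in these comparisons, which no analysis can undo once the answers have not been collected.

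The size depends on an adherence rate that the documents do not give; 4.5 to 18 of 45 at a visit corresponds to an assumed 10% to 40%, and further assumes that staff read the clause as an adherence condition. No effect on eNO, sVCAM or the recording of the feasibility outcome is claimed, and 7.2 should be described as lacking an adherence criterion, not as lacking any withdrawal rule.

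**What to change.** 1. Delete the RC2 condition in 8.6.1 and 10.5. State that CRF 5 and CRF 6 are completed for every randomized participant who attends and has not withdrawn, whatever the adherence or diary count.
2. In Modules A and B, replace the sentence that makes 30 diaries a condition of staying with a request to complete as many diaries as possible. The 30-diary threshold can remain as part of the feasibility definition in 14.2.
3. Correct the cross-reference to 7.2 in 8.4, and align the contents entry with the heading of 8.5.
4. Reconcile the refill condition in 8.4 with 8.5. Which rule governs the refill is for the investigators to decide; none is proposed here.

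The cost is text edits to 8.4, 8.6.1, 10.5, the contents and two leaflets, and a few more questionnaires.
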